#### Neurological status

Neurological status will be evaluated both prior to the surgery and throughout the study.

Neurological status is based on four types of measurements (sections): motor, sensory, reflexes, and straight leg raising. Each of the sections is comprised of a number of elements. Following scales will be used to evaluate neurological status: reflexes (0 = Absent or Trace, 1 = Hyper-reflexic, 2 = Normal), sensory function (Light Touch or Pin Prick L1 to S1), motor function (using 0-5 scores 0-5 whereas 0= Total Paralysis, 1 = Palpable or Visible Contraction, 2 = Active Movement, Gravity Eliminated, 3 = Active Movement, Against Gravity, 4 = Active Movement, Against Some Resistance and 5 = Active Movement, Against Full Resistance (full strength) and straight leg raise (positive = patient experiences radiating leg pain below the knee on elevating the leg between 15 and 70 with the knee extended, normal = no pain is experienced on elevating the leg between 15 and 70 with the knee extended).

Overall neurological success will be defined as maintenance or improvement in all sections (motor, sensory, reflex, and straight leg raising) for the time period evaluated. In order for a section to be considered a success, each element in the section must remain the same or improve from the time of the baseline evaluation to the time period evaluated. Therefore, if any one element in any section does not stay the same or improve, then a patient will not be considered a success for neurological status.

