**Table 3: Description of Procedures and Assessments at different time intervals**

Pre-operative visit (Baseline):	

• Written Patient Informed Consent /Data Release Form

• Demographic data

• Medical history

• Work status

• Pain medication

--------------------------------------------	------------------------------------------------------------------------------------------------------------------------------------------------------------------------------------------------------------

	
 
• VAS Back and leg pain
 
• ODI
 
• EQ-5D
 
• Neurological status
 
• AP & Lateral Radiographic Evaluation
 
• Imaging (MRI and/or CT Scan)
 
• Sagittal balance (in those sites where this assessment is Standard of care)
 
• DN4 for back and DN4 for leg**
 

Surgical procedure:	
 
• Surgery procedure data
 
• Surgery time
 
• Blood loss and Transfusion
 
• Device Models
 
• Adverse Events
 

Hospital stay and discharge: (Surgery = Day 0)	
 
• Length of hospital stay (in days)
 
• VAS Back and leg pain (at Day 2, the day the patient is considered recovered from the surgery(=SRD) and/or Day of discharge)
 
• Time in days to first ambulation
 
• Surgery Recovery Day
 
• Record pain medication
 
• Adverse Events
 

Postoperative assessment at 4w (<math>\pm 2w</math>): 3m (-1.5/+3m)	
 
• VAS Back and leg pain
 
• ODI
 
• EQ-5D
 
• Neurological Status
 
• Work Status and rehabilitation program
 
• Pain medication
 
• Adverse Events
 
• Sagittal balance (in those sites where this assessment is standard of care)
 
• DN4 for back and DN4 for leg (at 3m only)**
 

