## **E.3 Baseline procedures**

During the baseline visit the following data will be collected, patient demographics, medical history, comorbidities, surgery indication, pain medication, work status, imaging data. A standardized visual analogue scale (VAS, 0-10) will be used to evaluate the level of leg and back pain as perceived by the patient prior to surgery. Quality of life will be assessed having the patient completing the EQ-5D. Evaluation of how back or leg pain is affecting the patient's ability to manage in everyday life will be assessed using the Oswestry Disability Questionnaire (ODI). Neurological status; in case of a neurological abnormality, the neurological status will be assessed and documented. The measurement of Slip and Disk Height of the levels adjacent to the index level(s) will be collected by X-Ray, CT scan and/or MRI whichever is applicable at the site. The identification of neuropathic pain will be assessed by the DN4 questionnaire in the back and in the leg.

Sagittal Balance will be collected in those sites where it is standard of care by collecting an X-Ray (preferably this would be a long standing / full spine X-Ray (C7 + Femoral Head visible) or alternatively a short X-Ray with the femoral heads and top of lordotic segment visible).

AEs should be collected after patient signed consent/data release form.

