#### **E.6 Follow up requirements.**

The schedule for patient assessments and follow-up visits after surgery (with required windows) will be 4 weeks ( $\pm$  2 weeks), 3 months (-1.5/+3 month), 1 year ( $\pm$  6 month), 2 years ( $\pm$  6 month), 3 years ( $\pm$  6 month), 4 years ( $\pm$  6 month), 5 years ( $\pm$  6 month).

After the closure of the 5 year follow-up visit window patients will be automatically considered as terminated from the study.

All data will be collected via a secure web-based data entry system.

Treatment outcomes in terms of how back or leg pain is affecting the patient's ability to manage in everyday life will be assessed using the Oswestry Disability Questionnaire (ODI). Preferably, these ODI outcome measurements at 1, 3 months and 1, 2, 3, 4, 5 year follow up will be done by site staff different than the surgeon who operated the patient.

A standardized visual analogue scale (VAS, 0-10) will be used to evaluate the level of leg and back pain as perceived by the patient.

Quality of life will be assessed having the patient completing the EQ-5D.

The identification of neuropathic pain will be assessed by the DN4 questionnaire in the back and in the leg at 3 and 12 months follow up.

The measurement of Slip and Disk Height of the levels adjacent to the fused level(s) and fusion will be collected at 1 year follow up with either a CT scan or X-Rays. If no fusion is observed, 1 year after the surgery, further fusion follow up assessment will be at the discretion of the investigator.

Neurological status will also be documented. This is an AE if the patient did not have a neurological abnormality before.

Additional medical visits, Pain medication, work status and rehabilitation program will also be collected as part of overall patient follow up.

Sagittal Balance will be collected in those sites where it is standard of care by collecting an X-Ray (preferably this would be a long standing / full spine X-Ray (C7 + Femoral Head visible) or alternatively a short X-Ray with the femoral heads and top of lordotic segment visible).

Table 2 summarizes assessments and data (variables) to be collected in the electronic-CRFs throughout the study.

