6.9.2.2.2. Neurological success

Neurological status is based on four sections: motor, sensory, reflexes, and straight leg raising. Each of the sections is comprised of a number of elements.

6.9.2.2.2.1 Motor Function

For the motor function, the assessments are listed in ascending order of improving as indicated below:

0 = Total Paralysis

1 = Palpable or Visible Contraction

2 = Active Movement, Gravity Eliminated

This document is electronically controlled. Printed copies are considered uncontrolled.

Confidential

3 = Active Movement, Against Gravity

4 = Active Movement, Against Some Resistance

5 = Active Movement, Against Full Resistance (full strength) (Normal)

For the time period evaluated, for each of elements, if the score increases from baseline, the subject is considered "improved"; if the score remains the same as baseline, the subject is considered "maintained"; if the score decreases from the baseline, the subject is considered "deteriorated". In the situation where the score at baseline is 0 (Total Paralysis) and a postoperative visit is missing, or the score at baseline is missing and at a postoperative visit is 5 (Normal), the subject is conservatively considered as "maintained". For overall motor status, if at least one element has the status of "improved" and the rest are "maintained", then the overall motor status is considered "improved"; if all elements have the status of "maintained", then the overall motor status is "maintained"; if at least one element has the status of "deteriorated", then the overall motor status is "deteriorated."

6.9.2.2.2.2 Sensory function (Light Touch or Pin Prick L1 to S1)

For the sensory function, the assessments include absent, impaired and present (normal) which are listed in ascending order of improving. Let absent be 0, impaired be 1 and normal be 2. The same logic outlined in the motor function section will be used to first determine the change status of each element from the baseline and then the overall sensory status from the baseline. For each element, in the situation where the score at baseline is 0 (Absent) and a postoperative visit is missing, or the score at baseline is missing and at a postoperative visit is 2 (Normal), the subject is conservatively considered as "maintained".

6.9.2.2.2.3 Reflexes

For the reflexes, the assessments are listed as indicated below:

0 = Absent or Trace

1 = Hyper-reflexic

2 = Normal

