For each element, a change from 0 (Absent or Trace) to 2 (Normal) or 1 (Hyper-reflexic) to 2 (Normal) is considered improved while the other way around is considered deteriorated. No change is considered maintained. Any change from 0 (Absent or Trace) to 1 (Hyper-reflexic) is considered "diminished to hyperactive" while the other way around is considered "hyperactive to diminished". In the situation where the score at baseline is missing and at a postoperative visit is 2 (Normal), the subject is conservatively considered as "maintained". If none of element has the situation of "diminished to hyperactive" or "hyperactive to diminished", an overall evaluation of reflex will be summarized using the same logic outlined in the motor function section. Otherwise, there will be no overall evaluation.

6.9.2.2.2.4 Straight leg raise

For the straight leg raise, the assessments include positive and negative (normal). Let positive be 0 and negative be 1. The same logic outlined in the motor function section will be used to first determine the

This document is electronically controlled. Printed copies are considered uncontrolled.

Confidential

change status of each element from the baseline and then the overall straight leg raise status from the baseline. For each element, in the situation where the score at baseline is 0 (Positive) and a postoperative visit is missing, or the score at baseline is missing and at a postoperative visit is 1 (Negative), the subject is conservatively considered as "maintained".

Overall neurological success will be defined as maintenance or improvement in all sections (motor, sensory, reflex, and straight leg raising) for the time period evaluated. In order for a section to be considered a success, each element in the section must remain the same or improved from the time of the baseline evaluation to the time period evaluated. If at least one section is deteriorated, the overall neurological success will be defined as failure.

Summary statistics (frequencies) will be presented for status of each section and overall neurological success at each follow-up.

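### The protocol contradicts itself on whether a normal baseline neurological status is recorded, and the SAP scores a missing baseline only when follow-up is normal; if baselines are left blank, neurological success is biased upward.

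*Protocol*

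**What the plan says.** **Collection at baseline.** Protocol E.3, which describes the baseline visit, says: "Neurological status; in case of a neurological abnormality, the neurological status will be assessed and documented". Protocol B.1.3 carries no such condition: "Neurological status will be evaluated both prior to the surgery and throughout the study". The pre-operative entry in Table 3 (Description of Procedures and Assessments) lists "Neurological status" without qualification. The schedules in the Synopsis (Table 1) and E.7 (Table 4) mark it at baseline without a footnote.

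**Follow-up.** Protocol E.6 has neurological status documented at follow-up and adds: "This is an AE if the patient did not have a neurological abnormality before".

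**Scoring.** In SAP 6.9.2.2.2 the motor rule is that if "the score at baseline is missing and at a postoperative visit is 5 (Normal), the subject is conservatively considered as" *maintained*. For reflexes: "In the situation where the score at baseline is missing and at a postoperative visit is 2 (Normal), the subject is conservatively considered as" *maintained*. The sensory and straight-leg-raise rules follow the same pattern. *Deteriorated* requires a fall from the baseline score, and overall failure requires at least one deteriorated section. None of the four sections says what to do when baseline is missing and follow-up is abnormal. SAP 6.4 bases all analyses on observed data.

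**The concern.** A site that takes E.3 at its word leaves the baseline elements blank for a neurologically normal patient and still records scores at follow-up. The SAP then keeps or loses that patient according to the outcome. A normal follow-up is scored and can count towards success. An abnormal follow-up has no baseline to fall from, so it cannot be *deteriorated*. Yet a blank left under E.3 would mean that there was no abnormality, so the later finding is a real deterioration, and E.6 treats it as an adverse event.

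Taken alone, the rule for a normal follow-up is right: a patient who is normal afterwards cannot have worsened, whatever the baseline was. The fault is that the other half of the rule is absent. Calling the rule conservative does not fit, because it can only add successes.

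At stake is one of the endpoints under secondary objective 2, which SAP 6.1.3 has analysed by anterolateral and posterior group. The distortion depends on the share of patients who start normal and on the rate of new deficits. It could therefore differ between approaches.

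**Working it through.** The documents give no neurological success rate, so there is no figure to reproduce. The check has a logical part and an illustrative part.

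**Logic, for a patient with a blank baseline element**
- Follow-up normal: *maintained*, which counts towards success.
- Follow-up abnormal: no status. It cannot be *deteriorated*, so it cannot trigger the SAP's failure rule.

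The result is one-directional and identical in all four sections. It also applies to any baseline missing for other reasons, so correcting E.3 alone does not close it.

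**Illustration.** All rates are assumptions. Let *p* be the share of patients normal at baseline with nothing recorded, *f_n* their rate of new deficit, and *f_a* the rate of deterioration among patients with a recorded baseline.
- Successes: S = p(1 − f_n) + (1 − p)(1 − f_a). This is also the true success rate.
- Scored failures: F = (1 − p) f_a.
- Unscored: U = p f_n.
- Reported rate with unscored patients left out: S/(S + F) = S/(1 − U).

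Example with p = 60%, f_n = 8%, f_a = 10%: S = 0.6 × 0.92 + 0.4 × 0.90 = 0.912; F = 0.040; U = 0.048. Reported: 0.912/0.952 = 95.8%, against a true 91.2%. Of the 8.8% who truly fail, 4.8% go unscored.

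The last column is 350 × U, using the planned enrolment in Protocol B.7.

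| p | f_n | f_a | True % | Reported % | Bias (points) | Unscored of 350 |
|---|---|---|---|---|---|---|
| 20% | 2% | 2% | 98.0 | 98.4 | +0.4 | 1.4 |
| 20% | 5% | 5% | 95.0 | 96.0 | +1.0 | 3.5 |
| 20% | 10% | 10% | 90.0 | 91.8 | +1.8 | 7.0 |
| 50% | 2% | 2% | 98.0 | 99.0 | +1.0 | 3.5 |
| 50% | 5% | 5% | 95.0 | 97.4 | +2.4 | 8.8 |
| 50% | 10% | 10% | 90.0 | 94.7 | +4.7 | 17.5 |
| 80% | 2% | 2% | 98.0 | 99.6 | +1.6 | 5.6 |
| 80% | 5% | 5% | 95.0 | 99.0 | +4.0 | 14.0 |
| 80% | 10% | 10% | 90.0 | 97.8 | +7.8 | 28.0 |
| 40% | 5% | 10% | 92.0 | 93.9 | +1.9 | 7.0 |
| 60% | 8% | 10% | 91.2 | 95.8 | +4.6 | 16.8 |
| 70% | 15% | 10% | 86.5 | 96.6 | +10.1 | 36.8 |
| 0% (all baselines recorded) | – | any | 1 − f_a | 1 − f_a | 0 | 0 |

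**Effect on a comparison of approaches.** Two groups with the same true 95.0% would be reported as 96.0% and 99.0% if p were 20% in one and 80% in the other. Two groups with p = 50% and true rates of 98.0% and 90.0% (8.0 points apart) would be reported as 99.0% and 94.7% (4.3 points apart).

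**Effect of how the gap is filled.** If the unscored element is skipped and the patient still counts as a success, the reported rate is S + U. In the 70%/15%/10% case that is 97.0%, a bias of +10.5. If the patient is instead counted as a non-success, the reported rate is S and the bias is zero. The SAP does not say which applies.

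**The case against.** A reader might infer that baseline status is documented only when abnormal, that new deficits therefore cannot count as failures, and that success is overstated by construction. The documents do not support that.

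- E.3 is one awkwardly worded sentence against B.1.3, the pre-operative list and two schedule tables. Protocol E.11 also makes an assessment not performed at a visit a recorded deviation. If sites follow those passages, E.3 causes no bias. This stands: the defect is a contradiction, not a settled instruction to leave blanks.
- The case report form is filed separately (Protocol K.2). It may hold a no-abnormality entry that can be scored as normal. This stands, and the frequency of blanks cannot be judged from the documents.
- Protocol B.1.3 and G.1.2 and the SAP all require every element to be maintained or improved for success. An element with no status has not met that and could be counted as a non-success. This stands as a possible reading. It also shows the gap, because the SAP's failure rule is narrower than the protocol's definition of non-success.
- New deficits in previously normal patients are collected as adverse events under E.6, so they are not lost to safety reporting. True, but adverse events do not feed neurological success, and the summaries listed in SAP 6.10 include no neurological category.
- The endpoint is secondary and descriptive (Protocol B.4, SAP 6.2). True; this limits the severity but does not justify a rule that selects on outcome.

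**Conclusion.** Wrong as written; it should be fixed. Two points rest on the text alone. The protocol conflicts with itself on recording normal baselines, and the SAP resolves a missing baseline only when follow-up is normal.

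The upward bias is conditional. It requires that sites follow E.3 over the other passages, that blanks are treated as missing, and that patients left without a status are dropped or not counted as non-successes. Under those conditions and the assumed rates above, it runs from about +0.4 to +10 percentage points. Nothing in the documents narrows that range, and the E.3 contribution is zero if every baseline is recorded. The SAP gap remains for any other missing baseline. The primary endpoint, its equivalence test and the sample size are untouched.

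**What to change.** 1. **Protocol E.3.** Reconcile it with B.1.3, the pre-operative list and the schedules, so that all neurological elements are documented at baseline for every patient, normal findings included.
2. **SAP 6.9.2.2.2, baseline known to be normal.** Where the baseline record affirmatively shows no neurological abnormality, use the normal score (motor 5, sensory 2, reflex 2, straight leg raise 1), so that a later abnormal score is *deteriorated*. Do not apply this to every blank: a blank may be a missed examination, and scoring it as normal could turn a pre-existing deficit into a false deterioration.
3. **SAP 6.9.2.2.2, baseline truly unknown.** Exclude the element whatever the follow-up result, and state whether the patient stays in the denominator on the remaining elements. Report the number of unscored patients by approach. If many baselines are blank, the rate then describes mainly patients who had a recorded baseline, and the counts make that visible.
4. **Sensitivity analysis.** Count missing baseline with abnormal follow-up as failure, keeping missing baseline with normal follow-up as *maintained*.

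The cost is a few sentences in each document, with no new visits or procedures. The reported success rate may be slightly lower. Enrolment began in 2016, and Protocol F.1.2 has neurological status recorded directly on the case report form as source data, so blanks already collected may not be recoverable. Items 3 and 4 cover those patients.

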**Table 4: Summary of scheduled procedures and assessments**

	Baseline	Day of Surgery (D0) (2)	Hospital Stay and Discharge (3)			Follow up assessments					
			D2	SRD	DIS	4( $\pm$ 2)week	3(-1.5/+3)month	1 year ( $\pm$ 6 months)	2 year ( $\pm$ 6 months)	3 year ( $\pm$ 6 months)	4 year ( $\pm$ 6 months)
Data Release Form OR Informed Consent Form	X (1)										
Demographics	X										
Medical History	X										
Surgery Indication	X										
Pain medication	X		X	X	X	X	X	X	X	X	X
Imaging (X-Ray, MRI and/or CT Scan)	X										
VAS (4)	X		X	X	X	X	X	X	X	X	X
ODI	X					X	X	X	X	X	X
EQ-5D	X					X	X	X	X	X	X
DN4 in the back and DN4 in the leg	X						X	X			
Work status	X					X	X	X	X	X	X

Rehabilitation Program						X	X	X	X	X	X	X
Neurological status	X					X	X	X	X	X	X	X
X-Ray or CT Scan (5)							X	(X)	(X)	(X)	(X)	(X)
Sagittal Balance(6)	(X)					(X)						
Surgery and hospital data		X	X	X	X							
Adverse Events	X	X	X	X	X	X	X	X	X	X	X	X

- (1) Patient Informed Consent must be obtained prior to performing any study specific procedure
- (2) Day '0' (D0) is the day of the surgery, D1 is the first day after surgery, D2 the second and so on.
- (3) **SRD** = Surgery Recovery Day; **DIS** = Day of Discharge
- (4) VAS Intensity scores for Back and Leg pains.
- (5) CT scan or X-Rays at 1 year follow up. If no fusion is observed at 1 year follow-up, it will be at the discretion of the investigator to follow up if fusion can be observed (only if standard of care at the site).
- (6) Optional only if it is routine practice (standard of care) at the site

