6.9.3. Additional Analyses

1. Analyses for baseline information can be found in section 6.6.
2. Determine if there is a correlation between sagittal balance at baseline and the radiological findings (fusion) and the clinical outcomes at the follow-up visit, in those sites where this assessment is standard of care. Pearson correlation coefficient and 95% CI will be provided.
3. Hospital stay in days after the surgery when patients has been discharged from hospital will be summarized.
4. Days to first return to work will be summarized.
5. Sagittal balance parameters and change from the baseline if applicable will be summarized by visits in those sites where this assessment is part of standard of care. The parameters include pelvic incidence, sacral slope, pelvic tilt, and global lordosis angle.
6. Adjacent levels radiographic review will be summarized by visits if it is available. Instead of summarizing measurements of length of body and slip in millimeter, the percentage of slip or grade/type of spondylolisthesis, and disc relative height will be summarized due to zooming effect from x-ray and MRI.
7. Several subgroup analyses will be conducted based on Douleur Neuropathique 4 (DN4) scores (respectively for leg and back DN4 score) at baseline, 3-month and 12-month visit. Subgroups include:

This document is electronically controlled. Printed copies are considered uncontrolled.

Confidential

- Subjects with baseline $DN4 \geq 4$ and $DN4 \geq 4$ at 3-month follow-up
- Subjects with baseline $DN4 \geq 4$ and $DN4 < 4$ at 3-month follow-up
- Subjects with baseline $DN4 < 4$ and $DN4 \geq 4$ at 3-month follow-up
- Subjects with baseline $DN4 < 4$ and $DN4 < 4$ at 3-month follow-up
- Subjects with baseline $DN4 \geq 4$ and $DN4 \geq 4$ at 12-month follow-up
- Subjects with baseline $DN4 \geq 4$ and $DN4 < 4$ at 12-month follow-up
- Subjects with baseline $DN4 < 4$ and $DN4 \geq 4$ at 12-month follow-up
- Subjects with baseline $DN4 < 4$ and $DN4 < 4$ at 12-months follow-up

For each subgroup, the number and percentage of subjects will be provided. In addition, ODI, EQ-5D, VAS back and leg pain scores at baseline, at each follow-up and the improvement from baseline will be presented by the subgroups. Statistical comparison may be carried out for these subgroups analyses.

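### Adjacent-level slip and disc height may be read from MRI at baseline but not at 1 year, and the SAP's visit summaries correct for magnification without separating imaging modalities

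*Protocol*

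**What the plan says.** At baseline, Protocol E.3 allows three modalities and leaves the choice to the site: "The measurement of Slip and Disk Height of the levels adjacent to the index level(s) will be collected by X-Ray, CT scan and/or MRI". At 1 year, Protocol E.6 says that the same measurements, together with fusion, "will be collected at 1 year follow up with either a CT scan or X-Rays". MRI is not on the 1-year list.

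SAP 6.9.3 item 6 plans this analysis: "Adjacent levels radiographic review will be summarized by visits if it is available". The item drops millimetre values in favour of percent slip or grade/type, and adds that "disc relative height will be summarized due to zooming effect from x-ray and MRI". SAP 6.6 applies the same relative measures at baseline. Neither section says how readings from different modalities are to be kept apart or compared.

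The baseline images are listed in two forms. The protocol table describing procedures at each time interval has an AP and "Lateral Radiographic Evaluation" entry and, separately, "Imaging (MRI and/or CT Scan"). The summary schedule in E.7 has one row, "Imaging (X-Ray, MRI and/or CT Scan").

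**The concern.** Two visit summaries are like for like only if the measuring method is the same at both visits, or if the methods agree. Here the permitted methods differ. A patient read on MRI at baseline has to change modality at 1 year if E.6 is followed. A patient read on X-ray or CT may also change, because both are allowed at both visits.

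The SAP itself treats the type of image as relevant, since it gives zoom on X-ray and MRI as its reason for using relative measures. That deals with scale. Other possible sources of disagreement, such as patient position, imaging plane or choice of landmark, are not addressed.

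What is at stake is how adjacent-level findings are read. Protocol A.1.4 discusses adjacent segment disease as a concern after instrumented fusion, so readers will look at these summaries for signs of it. A systematic offset between modalities would look like progression or improvement.

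**Working it through.** The plan gives no figure on this point, so there is none to reproduce. The check compares the texts and adds one illustration.

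**Step 1: permitted modalities**

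| | Baseline (E.3) | 1 year (E.6) |
|---|---|---|
| X-ray | yes | yes |
| CT | yes | yes |
| MRI | yes | not listed |

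Of the six possible single-image pairings (three at baseline, two at 1 year), two keep the modality: X-ray to X-ray and CT to CT. The other four change it. This counts what is permitted; it says nothing about how often each pairing will occur.

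**Step 2: what the SAP corrects.** Percent slip and relative disc height are ratios taken within one image, so a pure magnification factor cancels. Anything that alters the ratio itself does not cancel.

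**Step 3: what the SAP leaves open.** Item 6 has no split by modality, no restriction to same-modality pairs and no sensitivity analysis. By contrast, for sagittal balance E.3 and E.6 name one modality, X-ray, at both visits and state a preferred view. No such rule is given for adjacent-level slip and disc height.

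**Step 4: could a common baseline image exist?** The procedures table lists baseline AP and lateral radiographs, so an X-ray may be available to pair with a 1-year X-ray. But E.3 lets the reading come from whichever modality applies at the site, and nothing requires it to be taken from that radiograph.

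**Step 5: illustration of size.** Let p be the share of patients whose modality changes in the same direction, and b the mean offset between modalities that remains after scaling, in percentage points of slip. With the same patients at both visits:

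apparent shift in the visit mean = p × b

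The documents give neither p nor b. Both are assumptions, shown over a range:

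| p | b = 0 | b = 1 | b = 2 | b = 5 |
|---|---|---|---|---|
| 0% | 0 | 0 | 0 | 0 |
| 25% | 0 | 0.25 | 0.50 | 1.25 |
| 50% | 0 | 0.50 | 1.00 | 2.50 |
| 75% | 0 | 0.75 | 1.50 | 3.75 |
| 100% | 0 | 1.00 | 2.00 | 5.00 |

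The shift is zero if no patient changes modality or if the modalities agree after scaling. Changes in opposite directions would partly cancel in the mean.

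**Step 6: if grade is reported instead.** Protocol B.1.3 puts Grade I below 25% and Grade II at 25 to 49%. Shifts of the size in the table would alter a grade only for readings near a boundary.

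**The case against.** The strongest reply is that this is a small descriptive item and that the plan claims little from it. Most of that reply stands.

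- **No change analysis is written.** Item 5 of SAP 6.9.3 names change from baseline for sagittal balance; item 6 does not. A reader might infer that a biased change estimate is planned. The text does not support that. The problem arises when someone compares the two visit summaries.
- **Modality is not ignored.** A reader might infer that the SAP pools raw readings from all images. It does not: the relative measures remove the scale difference. Whether any other difference remains, and how large it is, cannot be settled from the documents.
- **No approach difference is shown.** It is tempting to argue that image choice follows the site, that the site's preferred procedure follows the surgeon, and that a modality imbalance would therefore look like an effect of approach. E.3 does leave the modality to the site, and B.7 acknowledges user preference for procedures, but nothing links the two. The approach split in SAP 6.1.3 is tied to the primary endpoint and to secondary objectives 2 and 3, and item 6 specifies no comparison of approaches. SAP 6.6 does allow baseline summaries by approach.
- **The measure is not a listed endpoint.** Adjacent-level slip and disc height are absent from the endpoints in B.1.3 and from the additional measurements in B.1.4. The listed adjacent-level endpoint is secondary surgery, analysed by life table, and imaging modality does not enter it.
- **The baseline imaging entries can be read together.** One table lists images for the visit, E.3 says where one measurement may come from, and the schedule row is a condensed form. This is an ambiguity to clear up rather than a plain contradiction.

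None of these points supplies a rule that makes the baseline and 1-year summaries comparable.

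**Conclusion.** The point holds in a limited form. The permitted modalities differ between baseline and 1 year, and the SAP corrects for magnification only, so a comparison of the two visit summaries can mix a change of imaging method with a change in the spine. This rests on the wording of E.3, E.6 and SAP 6.9.3 item 6, and on the assumption that readers will compare the visits.

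The size is unknown. The illustration runs from 0 to 5 points of percent slip, and both of its inputs are assumed. The primary endpoint, the two equivalence hypotheses and the listed secondary endpoints are not touched. This is an inexpensive improvement to an additional analysis, not a threat to the study's conclusions.

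**What to change.** 1. In SAP 6.9.3 item 6, present the visit summaries by imaging modality.
2. If change from baseline to follow-up is reported, show it only for patients read on the same modality at both visits, with X-ray to X-ray and CT to CT separate. Give the number of mixed pairs by approach group and do not pool them with the rest.
3. Confirm that the modality of each reading is recorded. The case report form is filed separately (Protocol K.2), so this cannot be checked here. If it is not recorded, it may be recoverable from the source images, which Protocol E.8 places in the patient's records.
4. Reconcile E.3, the table of procedures at each time interval and the E.7 schedule, so that sites know which baseline image is to be measured.

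No new images are needed. The price is fewer pairs, smaller cells and possibly one added data field.
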